10.5 Randomization Procedures

Women will be randomized using a 2:1 ratio to one of the two arms, i.e. two women will be randomized to the study IVR arm for each woman randomized to the no IVR arm. Randomization will be stratified by site to ensure a 2:1 balance within each site. The randomization scheme will be generated and maintained by the SDMC. The SDMC will provide each study site with one set of randomization envelopes to be stored and used in the study clinic. Clinic staff will assign these envelopes in sequential order, by envelope number, to eligible participants. Additional envelopes will be provided to each site for the purpose of enrolling a greater number of participants per site if enrollment “slots” need to be shifted from one site to another during the course of the study.

Assignment of the randomization envelope is considered the effective act of participant enrollment/randomization. The randomization document contained within the envelope indicates the study arm (study IVR or no IVR) to which the participant is assigned. For participants assigned to the study IVR arm, this randomization document is the study prescription. Clinic staff will store assigned randomization envelopes and copies of the randomization document in the participants’ study charts.

10.6 Justification for the No IVR arm

Inclusion of a no IVR arm in this safety and adherence study will enable investigators to compare the incidence of AEs as well as changes in vaginal flora, sexual behavior and vaginal hygiene practices among women using the study IVR to that of women using no IVR.

10.7 Participant Accrual and Retention

Based on previous studies of vaginal products with similar eligibility requirements conducted at these 3 sites (i.e. HPTN 059), the accrual of 252 eligible participants with normal reproductive tracts is expected to require the screening of approximately 380 volunteers. The target for retention will be 95% of enrolled participants over the 16 weeks follow-up period. Therefore, it is anticipated that approximately 252 women will be enrolled in the study. Accrual is anticipated to take approximately 6 months and 10 months at the US and non-US sites, respectively.

10.8 Data Monitoring and Analysis

10.8.1 Study Monitoring Committee (SMC)

In addition to the safety monitoring done by the PSRT (described in Section 8.2), the MTN SDMC will prepare study progress reports and reports of AEs experienced by study participants (blinded to treatment assignment when feasible) for review by the MTN SMC. The SMC will conduct interim reviews of study progress (blinded to treatment assignment when feasible), including rates of participant accrual, retention, rates of adherence to study IVR use, and product safety. These reviews will take place approximately every 90 days, or as needed. At the time of these reviews, or at any other time, the SMC may recommend that the study proceed as designed, proceed with design modifications, or be discontinued.

10.8.2 Primary Analysis

When the use of descriptive statistics to assess group characteristics or differences is required, the following methods will be used: for categorical variables, the number and percent in each category; for continuous variables, the mean, median, standard deviation, quartiles and range (minimum, maximum). Within-arm assessment of the change from the baseline measurement to a follow-up measurement will be analyzed using McNemar's test (for categorical response variables) or the paired t-test or Wilcoxon signed-ranks test (for continuous variables). When use of formal testing to assess differences between the study IVR arm and the no IVR arm is required, the following methods will be used: for binomial response variables, chi-square tests and logistic regression; for continuous variables, t-tests and linear regression nonparametric methods if data are non-Normal. To assess the adequacy of the randomization, study IVR and no IVR participants will be compared for baseline characteristics including

demographics, pelvic examination, and laboratory measurements using descriptive statistics. Due to the small sample size, formal baseline comparisons will not be done.

Primary Safety Analysis

The primary aim of the study is to assess the safety and toxicity of the study IVR. First, an intent-to-treat (ITT) analysis will be performed where data from all visits are included. To assess safety, the number and the percentages of participants experiencing the safety or toxicity endpoint described in Section 10.2.1, will be presented by arm. For each arm, binomial rates will be presented along with their corresponding exact 95% confidence interval estimates. For assessing the difference between the arms, a non-inferiority bound will be computed using an exact one-sided 95% confidence interval for the difference in rates between the two arms (see Section II in Therapeutic Equivalence in Encyclopedia of Biopharmaceutical Statistics).⁶⁷ Second, a per-protocol analysis will also be performed since non-adherent women in the IVR arm that are included in the ITT analysis might potentially lower the rate of safety endpoints in the IVR arm. Therefore a per-protocol analysis, where visits of non-adherent women will be excluded from the analysis, will be used to explore the sensitivity of the conclusions obtained via the primary safety analyses based on the ITT dataset. For this analysis, all visits of adherent women (defined as using the product 50% of the time or more) will be included where comparison of safety rates between arms will be performed using generalized estimating equation methods to take into account that the 4-week visits are not independent within a participant.

The above primary safety analysis will be supplemented by the following additional analyses. Adverse events will be analyzed using MedDRA preferred terms. The number and percentage of participants experiencing each specific adverse event will be tabulated by severity and by relationship to study product (for the study IVR arm only). For the calculations in these tables, each participant's adverse experience will be counted once under the maximum severity or the strongest recorded causal relationship to study product. Finally, a listing of AEs reported to the DAIDS Medical Officer and the Population Council will provide details of the event including severity, relationship to study product, onset, duration and outcome.

Boxplots of local laboratory values will be generated for baseline values and for values measured during the course of the study. Each boxplot will show the 1st quartile, the median, and the 3rd quartile. Outliers, or values outside the boxplot, will also be plotted. If appropriate, horizontal lines representing boundaries for abnormal values will be plotted.

Primary Adherence Analysis

To assess adherence of women randomized to the study IVR arm, the proportion of participants who kept the study IVR inserted at all times during the first 12 weeks of follow-up will be calculated along with its 95% confidence interval. For women who are not completely adherent, the average period of time during follow-up when the study IVR was outside the vagina as well as the average number of removals of the study IVR

from the vagina will be computed. All enrolled women in the study IVR arm will be included in this analysis.

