7.9 Laboratory Evaluations

7.9.1 Local Laboratory Testing

Blood

- HIV-1 test (see Appendix II)
- Syphilis serology

Urine

- Qualitative hCG
- UA
- Urine culture

Pelvic Specimens

- Pap smear
- Vaginal pH
- Vaginal fluid for wet mount microscopy (saline for BV; KOH for vulvovaginal candidiasis)
- *Trichomonas vaginalis* test
- Herpes culture (if local standard of care)
- Gram stained smear of vaginal fluid, obtained from lateral vaginal wall (India site only)
- Cervical swab for NAAT for GC/CT

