7.9.2 Network Laboratory Testing

Blood

- HIV-1 confirmatory testing as needed (see Appendix II)
- Plasma archive

Pelvic Specimens

- Vaginal flora assessment (quantitative vaginal fluid cultures-US sites only)
- Biofilm assessment of used study IVRs (US sites only-may include culture and/or other techniques)
- Gram stained smear of vaginal fluid, obtained from lateral vaginal wall (US sites only)
- Cervical swab for innate factors (US sites only)

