10.4 Sample Size

10.4.1 Safety Endpoints

The proposed total sample size is N=252 randomized into 2 arms: 168 and 84 women in the study IVR and no IVR arms, respectively. Given that assessing adherence to the study IVR is a primary objective, and that this can only be assessed in the study IVR arm, a 2:1 randomization was selected to increase the precision on estimates of adherence and acceptability. A 2:1 randomization will slightly decrease the power for the comparison of safety profiles between the study IVR and no IVR arms, but the decrease in power is not substantial. Participants who are non-adherent to the study product and/or the study visit schedule will not be replaced.

For the study IVR arm, if the true rate of a given toxicity endpoint is 5%, 168 women provide 80% power to exclude safety and toxicity endpoint rates greater than 10.0%, where the safety and toxicity endpoints for a woman are defined as the occurrence of the safety endpoint during follow-up, that is the occurrence during follow-up of evidence of Grade 2 or higher genitourinary events as defined by the DAIDS AE Grading Table, Version 1.0, Dec 2004 (clarification dated August 2009), Addendum 1 (Female Genital Grading Table for Use in Microbicide Studies).

For the no IVR arm, if the true rate of a given safety and toxicity endpoint is 5%, 84 women provide 80% power to exclude safety and toxicity endpoint rates greater than 13.3%.

The safety and toxicity rates of women using the study IVR and the rates for those not using the study IVR will be formally compared. A sample size of 252 women with a 2:1 randomization (i.e. 2 IVR : 1 no IVR) will assure with 80% power that a 95% confidence interval for the difference between the study IVR and no IVR safety and toxicity rates has an upper limit no more than 6.9% when the true toxicity rates for study IVR and no IVR are both 5%. The above calculations have been performed assuming true rates of toxicity of 5%. However, it is anticipated that the true rates are smaller than 5%. If this is the case, the above power computations are conservative and the actual power will be slightly higher. Table 8 displays 95% confidence interval upper bounds for different assumptions on the safety and toxicity rates in the IVR and no IVR arms. These bounds correspond to non-inferiority bounds computed using an exact one-sided 95% confidence interval for the difference in rates between the two arms as described in the Primary Safety Analysis.

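### Randomization is stratified by site, but the primary safety bound and the Nugent comparisons are specified without site: a modest loss of precision, and less protection where the 2:1 balance within site is lost

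*Protocol*

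**What the plan says.** Protocol section 10.5: "Randomization will be stratified by site to ensure a 2:1 balance within each site". Section 10.1 plans 150 women in Pune (100 ring, 50 no ring) and 102 at two US sites combined (68 and 34), with competitive enrollment between the US sites.

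For the primary safety comparison, section 10.8.2 says that "a non-inferiority bound will be computed using an exact one-sided 95% confidence interval for the difference in rates between the two arms". The sample-size section, 10.4.1, uses the same interval for Table 8: "These bounds correspond to non-inferiority bounds computed using an exact one-sided 95% confidence interval for the difference in rates between the two arms". It claims that 252 women "will assure with 80% power that a 95% confidence interval" for the difference "has an upper limit no more than 6.9% when the true toxicity rates for study IVR and no IVR are both 5" percent. It adds that "it is anticipated that the true rates are smaller than 5" percent.

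Section 10.8.3 compares Nugent shifts between arms by a Fisher exact test, and Nugent change scores by an unpaired t-test or Mann-Whitney test. Neither uses site. The slides are read in different places: section 7.9.1 lists for local laboratories "Gram stained smear of vaginal fluid, obtained from lateral vaginal wall (India site only", and section 7.9.2 lists for the Network Laboratory "Gram stained smear of vaginal fluid, obtained from lateral vaginal wall (US sites only".

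The per-protocol safety analysis (10.8.2) leaves out the visits of non-adherent women, with adherence defined as ring use at least half of the time, and compares arms by GEE. The behavioral measures (10.8.3) also use GEE. Section 10.8.2 names logistic and linear regression as general methods. None of these models has a covariate list, so site is neither included nor excluded there.

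**The concern.** An analysis normally reflects the factor that stratified the randomization. If it does not, differences between sites stay in the error term and the interval is wider than it needs to be. Here the pooled methods are named outright: a two-sample exact bound, a Fisher test and a two-sample t-test or Mann-Whitney test have no place for a site term. A later analysis plan would have to override them, not merely fill in a detail.

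Two things are at stake. The first is the width of the safety bound and the sensitivity of the Nugent comparisons. The second is balance. Stratified randomization keeps the country mix equal between arms only in the full randomized set. The per-protocol analysis and the Nugent subsets defined by baseline status do not keep that guarantee.

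**Working it through.** **Inputs.** 168 vs 84 women; India 100/50 and US 68/34 (10.1); both true rates 5%, one-sided 95% limit, 80% power, stated bound 6.9 points (10.4.1). Country-specific event rates are not given and are assumed below. The two US sites are treated as one stratum because their split is not fixed.

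**Reproducing the plan's figure.** Enumerating all outcomes of Bin(168, 0.05) and Bin(84, 0.05), the 80th percentile of the unstratified one-sided 95% Wald limit is 6.87 points, and the probability that the limit is at most 6.9 is 0.807. A Newcombe limit gives 6.70 points and 0.814. The stated 6.9 is therefore consistent with an unstratified bound. The exact interval of the cited reference was not recomputed.

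**Effect of stratifying the primary bound.** Let w be each country's share: India 150/252 = 0.595, US 102/252 = 0.405.

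- Crude variance: p(1-p)(1/168 + 1/84). At p = 0.05 this is 0.0475 × 0.017857 = 0.000848, so SE = 0.02912.
- Stratified variance: sum over countries of w² p_k(1-p_k)(1/n_ring + 1/n_none).
- With exact 2:1 allocation in each country, the crude and size-weighted differences are the same number. Only the SE changes, and the proportional reduction in variance is w_I × w_US × d² / [p(1-p)] = 0.241 d² / [p(1-p)], where d is the country gap.
- Stratified bound = 6.9 × √(variance ratio).

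| India / US rate (overall 5%) | Stratified SE | Variance saved | Bound | Worth in women |
|---|---|---|---|---|
| 5% / 5% | 0.02912 | 0% | 6.90 | 0 |
| 4% / 6.5% | 0.02908 | 0.3% | 6.89 | 1 |
| 3% / 7.9% | 0.02894 | 1.2% | 6.86 | 3 |
| 2% / 9.4% | 0.02871 | 2.8% | 6.80 | 7 |
| 1% / 10.9% | 0.02839 | 5.0% | 6.73 | 13 |
| 0% / 12.3% (limiting case) | 0.02797 | 7.7% | 6.63 | 21 |

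Simulation of 200,000 trials with Wald limits agrees: the 80th percentile moves from 6.87 to 6.83, 6.77 and 6.73 for the 3%, 2% and 1% India rows. Coverage of the crude limit was 96.8% to 97.1% against a nominal 95%.

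**Commoner outcomes.** Section 10.4.4 plans Nugent shifts at 30%. Using the same formula and the whole-trial country shares as an approximation: 30% overall with a 20-point gap, 0.241 × 0.04 / 0.21 = 4.6%; 30% with a 30-point gap, 10.3%; 50% with a 30-point gap, 8.7%.

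**Per-protocol country mix.** Control women have no ring to be non-adherent to, so exclusions fall on the ring arm alone. Section 10.4.2 anticipates that adherence may differ between India and the US. Assume adherence, as defined for this analysis, of 95% in India and 70% in the US, with no ring effect:

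- Ring arm retained: 95 Indian and 47.6 US women; India share 95/142.6 = 66.6%, against 59.5% in controls.
- Shift in the crude difference = 0.071 × (India rate - US rate): 0.071 × (2 - 10) = -0.6 points, or 0.071 × (5 - 25) = -1.4 points.

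With adherence 90% and 80%, India's share is 90/144.4 = 62.3% and the shifts are -0.2 and -0.6 points. Negative shifts favor the ring. The sign reverses if either country contrast reverses.

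**Nugent subsets.** Section 10.4.4 expects 138 women normal and 114 abnormal at enrollment. The 2:1 ratio within site is not guaranteed in either group, and reader and country coincide. Baseline status precedes randomization, so this imbalance is chance only, but a pooled test leaves it uncorrected.

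**The case against.** The strongest reply is that nothing in the primary analysis is wrong. The crude and weighted differences coincide under 2:1 allocation within site, the crude limit is conservative, and Table 8 is built on the same interval, so design and analysis agree. This stands. A reader might infer that ignoring site biases the intent-to-treat bound or makes it wider than the sample-size section promised. The documents support neither.

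A reader might also expect a gain of 8.5 to 12% of variance. That needs, for example, India/US rates of 5%/25% or 5%/30%. These imply overall rates of 0.595 × 5 + 0.405 × 25 = 13.1% and 0.595 × 5 + 0.405 × 30 = 15.1%. Table 8 extends to 15%, but section 10.4.1 expects rates below 5%. No non-inferiority margin is stated, so a shift of 0.1 or 0.2 points changes no decision.

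Stratifying the safety bound also has a cost. At 5%, 84 × 0.05 = 4.2 control events are expected. If the 34 US controls split evenly, each US site expects 17 × 0.05 = 0.85. A stratified score bound is asymptotic, and with counts this small that is a reason not to displace the exact bound.

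It is also too much to say that every arm comparison ignores site. The GEE and regression models are silent on covariates, which an analysis plan may settle.

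For Nugent results, each woman's slides go to one laboratory, so a constant reading shift partly cancels in change scores. It need not cancel in shifts across the cut-off of 3. The protocol's remarks on heterogeneity concern adherence and acceptability, not safety. That limits their weight for the primary bound, but adherence is exactly what drives the per-protocol exclusions.

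**Conclusion.** The point holds as a modest one. The stratification factor is absent from three comparisons whose methods are fixed in the text: the primary safety bound, the Nugent shift test and the Nugent change-score test. For the primary bound the loss is zero if the countries are alike and reaches about 0.2 points at an 11-fold country contrast; the pooled result remains valid. The potential gain for Nugent outcomes is larger in relative terms, but it depends on a country gap of 20 to 30 points, which is assumed.

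The better reason to use site is balance. The per-protocol analysis is meant to test whether the intent-to-treat conclusion is robust, and its exclusions can change the country mix of the ring arm alone. The shifts shown are illustrations under assumed adherence and event rates, not predictions. Adjusting for site would remove the country-mix part of that bias, not any other selection effect of excluding non-adherent women.

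**What to change.** 1. Keep the exact pooled one-sided 95% bound as the primary safety result. Prespecify beside it, as a sensitivity analysis, a site-stratified risk difference (Mantel-Haenszel weights) with a stratified Miettinen-Nurminen one-sided 95% upper bound.
2. Replace the pooled Nugent Fisher test with an exact Cochran-Mantel-Haenszel test stratified by site, and the change-score t-test or Mann-Whitney test with a linear model including site or a van Elteren test.
3. State that site is a covariate in the per-protocol safety GEE and in the behavioral GEE models.

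The cost is wording and a little more analysis. No data collection changes, and the sample size and Table 8 stand because the primary bound is unchanged. The stratified safety bound is asymptotic with few events and should be labelled so.

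### The per-protocol safety check changes the unit and the method along with the analysis set, so a difference from ITT could not be attributed to non-adherence

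*Protocol*

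**What the plan says.** Section 10.4.1 of the protocol sets the unit: "the safety and toxicity endpoints for a woman are defined as the occurrence of the safety endpoint during follow-up". Each woman contributes one yes or no, for any Grade 2 or higher genitourinary event. Table 8 is on that scale.

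Section 10.8.2 (Primary Safety Analysis) keeps this unit for ITT. It states that "the number and the percentages of participants experiencing the safety or toxicity endpoint described in Section 10.2.1, will be presented by arm" and that "a non-inferiority bound will be computed using an exact one-sided 95% confidence interval for the difference in rates between the two arms".

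The same section adds a per-protocol analysis because non-adherent women in the IVR arm could dilute that arm's event rate. Its stated purpose is that it "will be used to explore the sensitivity of the conclusions obtained via the primary safety analyses based on the ITT dataset". Its data are described thus: "all visits of adherent women (defined as using the product 50% of the time or more) will be included". Its method is that "comparison of safety rates between arms will be performed using generalized estimating equation methods to take into account that the 4-week visits are not independent". The section states no per-woman proportion, no bound and no link function for the per-protocol set.

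On the rates to expect, Section 10.4.1 says only that "it is anticipated that the true rates are smaller than 5" per cent. The one lower rate in Table 8 is 1%.

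**The concern.** A sensitivity analysis for non-adherence should vary who is analysed and hold everything else fixed. Here three things move together: the set (all women to adherent women), the unit (woman to 4-week visit) and the method (exact bound on a risk difference to GEE). If the two results differ, the reader cannot tell whether adherence, event duration or the effect scale is responsible. If they agree, the agreement may be accidental.

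In this trial dilution by non-use would make the ring look safer than it is. The per-protocol result is the protocol's own safeguard against that, so it needs to be readable beside the ITT result.

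The within-woman correlation that GEE is brought in to handle arises only because the unit was changed. One outcome per woman needs no such correction.

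**Working it through.** **Inputs.** 168 IVR and 84 no-IVR women, planning rate 5% in both arms, upper limit 6.9% with 80% power (Section 10.4.1); a 1% rate in Table 8; four follow-up visits per woman (Section 4.5). The protocol gives no figure for the share of IVR women who will meet the 50% use rule. I assume 80% to 100% (134 to 168 women). The 80% is borrowed from Section 10.4.2, where it refers to keeping the ring in.

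**Step 1: the plan's own figure is per woman.** The 80th percentile of the one-sided 95% Wald upper limit, enumerating both binomials at 5% and 5% with 168 and 84 women, is 6.87%, against the stated 6.9%. The normal formula gives (1.645 + 0.842) × √[0.05 × 0.95 × (1/168 + 1/84)] = 7.2%. The benchmark is therefore a difference in per-woman risks.

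**Step 2: effect of the unit, with visits coded by presence.** If a share p of women have an event and each event is present at k of 4 visits, the visit-level rate is p × k/4.

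- Equal risk, 5% and 5%, IVR events spanning 2 visits and no-IVR events 1: rates 0.05 × 2/4 = 2.5% and 0.05 × 1/4 = 1.25%. Odds ratio = (0.025/0.975)/(0.0125/0.9875) = **2.03**. The per-woman difference is zero.
- Doubled risk, 10% and 5%, IVR events spanning 1 visit and no-IVR events 2: rates 0.10 × 1/4 = 2.5% and 0.05 × 2/4 = 2.5%. Odds ratio = **1.00**. The per-woman difference is 5 points.

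Spans that differ by arm are plausible: Section 9.2 has the ring removed for some findings, and the control arm has no ring to remove.

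**Step 3: the same cases with visits coded by new onset.** If each event counts only at the visit where it first appears, the rate is p/4. The first case becomes 1.25% and 1.25%, odds ratio 1.00. The second becomes 2.5% and 1.25%, odds ratio 2.03, close to the per-woman odds ratio (0.10/0.90)/(0.05/0.95) = 2.11. The distortion in Step 2 thus depends on presence coding. The absolute scale still changes: a 5-point excess per woman becomes 1.25 points per visit.

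**Step 4: arms with no events.** With a common per-woman rate p, P(no events in 84) = (1 − p)^84, and P(at least one arm empty) = 1 − [1 − (1 − p)^84] × [1 − (1 − p)^168].

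| Rate p | No events in 84 | At least one arm empty, 168 v 84 | Same, 134 v 84 |
|---|---|---|---|
| 5% | 1.3% | 1.4% | 1.4% |
| 3% | 7.7% | 8.3% | 9.3% |
| 2% | 18% | 21% | 24% |
| 1% | 43% | 54% | 58% |

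Under a logit or log link, an empty arm leaves no finite arm effect.

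**Step 5: the per-woman bound in the per-protocol set.** With 134 and 84 women, the normal formula gives 7.5% at 5% and 5% (7.2% for 168 and 84), and 3.4% at 1% and 1% (3.3%). An exact bound exists even when an arm is empty. For example, 2 of 134 against 0 of 84 gives an upper limit of 12.9% with the unconditional bound ordered by the raw difference. That version is conservative: it gives 13.6% in the Step 1 setting, so Table 8 was not built with it.

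**The case against.** The strongest reply is that this is an exploratory check. The primary ITT analysis keeps the per-woman endpoint and the exact bound, and nothing stops a statistical analysis plan from also tabulating a per-woman per-protocol rate. Link, working correlation, visit coding and the handling of interim-visit events (Section 7.6) are ordinary content for that plan. With onset coding, Step 3 shows the relative effect is largely kept. All of this stands, and it limits the weight of the point. What it leaves in place is that the protocol text itself fixes a visit-level GEE as the per-protocol comparison.

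Three stronger readings are tempting, and the document does not support them.

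- A reader might infer that the GEE will often be impossible to fit at the rates expected. The protocol says only that rates should be below 5%. The chance of an empty arm is 3.3% at 4% and 8% at 3%, and it passes one half only near 1%, which is a row of Table 8 and not a stated expectation. It also depends on the link. An identity-link GEE with 4 IVR events and none in controls gives a finite difference of 4/672 = 0.60 points per visit (robust SE 0.29, probably too small because the empty arm adds no variance).
- A reader might infer that the 50% product-use rule removes the whole no-IVR arm. Section 10.8.2 aims the rule at non-adherent women in the IVR arm and goes on to compare the arms, so that cannot be the intent. The wording merits a clarifying clause.
- A reader might infer that the per-visit result would be misjudged against Table 8. The protocol does not say it will be read that way, and it sets no non-inferiority margin.

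**Conclusion.** The point holds in a narrow form. The per-protocol analysis cannot serve its stated purpose cleanly, because unit and method change together with the analysis set. Under presence coding the distortion can run either way: an odds ratio of about 2.0 with no difference in per-woman risk, or 1.0 with a doubled risk. Those two figures rest on assumed event spans of one and two visits, which the protocol does not give, and they disappear under onset coding. The estimability problem is conditional on a logit or log link and on the true rate: about 1% of trials at 5%, 8% at 3%, 21% at 2% and 54% at 1%. The primary ITT result is untouched, so this is a minor point, worth making because the remedy costs almost nothing.

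**What to change.** In Section 10.8.2, define the per-protocol set as IVR-arm women who used the ring at least 50% of the time plus all no-IVR women. For that set, report by arm the proportion of women with at least one Grade 2 or higher genitourinary event, and the same exact one-sided 95% upper bound on the difference as for ITT. Keep any visit-level GEE as a supplementary analysis.

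The cost is a sentence or two of text and a second run of a method already needed for ITT. The loss of precision from the smaller set is slight (7.2% to 7.5% in Step 5 if 134 IVR women qualify). The one downside is that visit-level information is not used in the main per-protocol result.

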6.5 Participant Counseling

Participants in Group A will receive study IVR adherence counseling at the Enrollment, 4-Week, and 8-Week Visits. Site staff will counsel participants to refrain from removing the ring (except as directed) and from using concomitant vaginal products and/or devices as described in Section 6.7.1. Site staff will also provide counseling for re-insertion in case of ring removal/expulsion.

The site staff will counsel participants to remove the IVR immediately and contact study site staff if they experience a rash, itching, or other skin trouble, joint pain, or difficulty breathing as these may be signs of an allergic reaction.

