10.3 Study Hypotheses

MTN-005 hypothesizes that the study IVR will be safe and will be used as directed by US and non-US women over 12 weeks of use.

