10.4.2 Adherence Endpoints

Adherence will be measured by the percentage of women who keep the IVR inserted in the vagina over the course of 12 weeks. Adherence can only be assessed among the 168 women randomized to the study IVR arm. A sample size of 168 women will provide a precision of 6.4% (i.e. half-width of the 95% exact confidence interval) assuming an observed adherence of 80%. Substantial heterogeneities in adherence between the Indian and the US sites might be observed in which case adherence will be estimated separately for Indian and US women. For the Indian site, a sample size of 100 women using the study IVR will provide a precision of 8.3% assuming an observed adherence of 80% while this precision would be 10.2% with a sample size of 68 US women using the study IVR.

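### The primary adherence proportion measures uninterrupted ring use for any reason, so it cannot alone answer the stated hypothesis that the ring is used as directed

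*Protocol*

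**What the plan says.** **Measure.** Protocol Section 10.8.2 (Primary Adherence Analysis) states that "the proportion of participants who kept the study IVR inserted at all times during the first 12 weeks of follow-up will be calculated" with a 95% confidence interval. Women outside that group are treated as not completely adherent; for them the average time with the ring out and the average number of removals are computed. On the denominator: "All enrolled women in the study IVR arm will be included in this analysis". Section 10.4.2 describes adherence in the same way, as the percentage of women who keep the ring in over 12 weeks.

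**Hypothesis.** Section 10.3, repeating Section 2.7.1, is that "the study IVR will be safe and will be used as directed by US and non-US women over 12 weeks of use".

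**Instruction to participants.** Section 6.5: "Site staff will counsel participants to refrain from removing the ring (except as directed"; the sentence goes on to other vaginal products.

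**Removals that the protocol itself directs.**
- Section 6.5: immediate removal by the participant if signs of a possible allergic reaction appear.
- Section 9.2: removal for confirmed deep epithelial disruption, for generalized erythema or severe edema, and for cervicitis; a hold if certain milder findings worsen.
- Sections 7.5.1, 7.5.2 and 9.4: discontinuation for HIV seroconversion, pregnancy or clinical reasons.

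**Data.** Section 7.8.1 has the questionnaires ask whether the ring was out, whether it was removed or expelled, under what conditions, and whether it went back in.

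**The concern.** The hypothesis and the statistic ask different questions. Use as directed concerns whether women followed instructions. Kept in at all times concerns whether the ring was ever out. The two differ for every woman whose ring came out because staff or the protocol said so: she complied, yet she falls in the not-completely-adherent group.

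Two things follow. First, a reader of the single proportion cannot separate unwillingness or inability to use the ring from clinician-ordered removal. Section 2.7.2 says the study is designed to assess use and non-use and the reasons, but Section 10.8.2 plans only the overall number of removals and time out, with no split by reason. Second, the two primary endpoints become linked. A genital finding that counts toward the safety endpoint may also trigger removal under Section 9.2, so more such findings lower the adherence figure even if behaviour is unchanged. Adherence is one of two primary objectives, and Section 10.4.1 gives it as the reason for 2:1 randomization.

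**Working it through.** **1. The plan's own precision.** Section 10.4.2 states: "A sample size of 168 women will provide a precision of 6.4" percent, defined as the "half-width of the 95% exact confidence interval) assuming an observed adherence of 80" percent. For India "a sample size of 100 women using the study IVR will provide a precision of 8.3" percent, and for the US "this precision would be 10.2% with a sample size of 68 US women using the study IVR".

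Clopper-Pearson two-sided 95% interval, half-width = (upper − lower)/2:

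| Women | Count near 80% | Half-width (points) | Stated |
|---|---|---|---|
| 168 | 134 (interval 72.9% to 85.6%) | 6.34 | 6.4 |
| 100 | 80 | 8.26 | 8.3 |
| 68 | 54 | 10.19 | 10.2 |

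The stated figures reproduce when rounded up to one decimal. No stated number is wrong.

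**2. Classification under the two readings.**

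| Woman | Inserted at all times | Used as directed |
|---|---|---|
| Ring never out | adherent | adherent |
| Out only on staff or protocol direction | not completely adherent | adherent |
| Took it out on her own decision | not completely adherent | not adherent |

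Only the second row differs. Expulsions are a separate matter, taken up under the objection.

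**3. Size, by assumption.** The protocol gives no rate of directed removal. Let d of n = 168 women have one, suppose that 80% of the remaining n − d keep the ring in throughout, that no woman with a directed removal also took the ring out on her own, and that no data are missing.

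- Stated measure: 0.80 × (n − d) / n
- As-directed measure: [0.80 × (n − d) + d] / n
- Gap: d / n, whatever value replaces 80%

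| d | Stated measure | As-directed measure | Gap (points) |
|---|---|---|---|
| 8 (about 5%) | 128/168 = 76.2% (95% CI 69.0 to 82.4) | 136/168 = 81.0% (74.2 to 86.6) | 8/168 = 4.8 |
| 17 (about 10%) | 121/168 = 72.0% (64.6 to 78.7) | 138/168 = 82.1% (75.5 to 87.6) | 17/168 = 10.1 |

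At d = 2 the gap is 2/168 = 1.2 points. It passes the planned 6.4 points only from d = 11 (0.064 × 168 = 10.8; 11/168 = 6.5%). If some women with a directed removal also took the ring out on their own, the gap shrinks in proportion.

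**The case against.** The strongest reply is that uninterrupted use is the intended endpoint. Section 6.1 has the ring in place for 12 consecutive weeks. Section 10.2.1 counts voluntary and involuntary removal together with time without the ring. Section 2.7.2 argues that a ring delivering an HIV prevention agent would probably have to be worn continuously, so time out is lost coverage whoever ordered it. All of this stands. It supports keeping the stated proportion, and a reader who infers that the measure is an error to be replaced goes beyond the documents. It does not make that proportion an answer to the hypothesis in Section 10.3.

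The size is also open to challenge. Section 10.4.1 plans on a 5% rate for the whole Grade 2 or higher genitourinary endpoint and expects less, Section 9.1 expects no toxicity, and most findings in Section 9.2 let ring use continue. Directed removal also has other sources, such as pregnancy or possible allergy, so the safety rate is not a strict ceiling. Still, 5% may well be high and 10% more so.

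A replacement measure that stopped the clock at staff-directed discontinuation would be debatable too. A woman whose ring is withdrawn early could count as fully adherent, which might hide poor tolerability. Expulsion raises a similar question, since a woman who rinses and re-inserts as instructed has followed directions. Both argue for separate rows rather than one new number.

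Finally, because all enrolled women are in the denominator, a reader might infer that those lost before week 12 pass as fully adherent when no removal is reported. The protocol does not say so. It is silent on how incomplete records are classified, which is commonly left to the SAP, and full inclusion is not an error.

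**Conclusion.** The mismatch is real and narrow. Sections 10.4.2 and 10.8.2 define uninterrupted ring use for any reason; Sections 6.5 and 10.3 speak of use as directed; and the protocol directs removals that the definition then scores as non-adherence. The planned summaries cannot separate the two.

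How far the estimate would move cannot be fixed from the protocol. In the illustration with 8 of 168 women it is 4.8 points (76.2% against 81.0%), somewhat below the planned half-width of 6.4 points; at very low rates it would hardly matter. The illustration rests on the assumed rate, on 80% uninterrupted use among the other women, and on no overlap between directed and self-initiated removal.

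The proportion is descriptive and carries no success threshold, so no decision rule is affected, and no stated figure is wrong. The conclusion does not depend on missing data and questions none of the clinical rules for removal.

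**What to change.** Reconcile Sections 10.4.2 and 10.8.2 with Sections 6.5 and 10.3 as follows.

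1. Keep the any-reason uninterrupted-use proportion as stated, and label it as such.
2. Report beside it, with an exact 95% confidence interval, an as-directed proportion in which removals directed by staff or the protocol do not count as non-adherence. State that discontinuation at the participant's own request, which Section 9.4 also lists, is not a directed removal.
3. Show the number of women with directed temporary holds and with directed permanent discontinuations as separate rows, so that early withdrawal of the ring is not hidden inside the as-directed figure.
4. Split the number and duration of removals into directed, voluntary and expulsion. A reader who regards a re-inserted expelled ring as use as directed can then see how many women that concerns.

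The cost is analysis wording and a few table rows. Section 7.8.1 already collects the conditions of removal, so no new visit or assessment is needed, and sample size and randomization are unchanged.
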